Protocol

Effectiveness in Preventing Surgical Site Infection by Using Prophylactic Occlusive Ionic Silver-containing Dressing in Abdominal Colorectal Surgery Patients – Randomized Controlled Trial

Principal investigator: [name] [name], Surgery Department, PMH

Co-investigators: [name], NC, Central Nursing Division (Wound & Stoma Care), PMH and

[name] [name], Central Nursing Division (Wound & Stoma Care), PMH

Abstract

Background: Ionic silver-containing dressing has been proven as a broad spectrum antimicrobial agent to reduce inflammation of wounds and promote healing. However, surgical incisions are usually dressed with conventional gauze dressing in colorectal surgery.

Objective: To compare the effectiveness in preventing surgical site infection (SSI) by using conventional gauze dressing and occlusive ionic silver-containing dressing.

Methods: This is a single-blind two-arm parallel randomized controlled trial on occlusive ionic silver-containing dressing conducted in Surgery Department of Princess Margaret Hospital. Two hundred patients who undergo emergency or elective abdominal colorectal surgery will be recruited and randomly assigned to have the surgical incisional wound dressed with conventional gauze dressing or occlusive ionic silver-containing dressing. Subjects will be assessed for SSI on day 3, 15 and 30 after operation in a clinical visit followed by phone interviews.

Background

Surgical site infections

According to a Clean Care is safer programme by World Health Organization(WHO), the second most frequent and surveyed health care-associated infections in high-income countries is surgical site infections (SSI). The highest SSI is the colorectal surgery with 9.5% interlude per operations [1]. SSI develop negative influence on patient outcome, such as burden the morbidity, mortality and extra expenses to health care system. The length of stay increased 9.7 days due to SSI in 2005 in USA, and more expenses spend on the antibiotics and the advanced dressing materials [1]. Patient suffered from SSI will double the mortality rate in USA with increased cost and readmission for the treatment.

Modern dressing

There are many different treatment and dressing options for health care providers for wound care. The dressings with advanced technology become more popular in recent days. Many studies show the importance of moist wound dressing to enhance the wound healing process. It can provide a moist wound environment, absorb the excess exudate, move away the microorganism and prevent their replication, and provide a barrier from the external environment than the conventional gauze dressing [2-4]. Besides, a recommendation from the UK's National Institution for Health and Clinical Excellence (NICE) suggest that all surgical incision wound should be dressed with low-adhesive dressing for at least 3-5 days after operation [5]. And a journal published in CINAHL Information

Silver dressing RCT – protocol (Version 5; 14 September 2017)

System stated that the use of dressing with moist wound healing effects can help to reduce the SSI rate by 50% that the conventional gauze [6]. On the other hand, there are studies commended that there are no significant different in prevention of SSI with the use of moist wound dressing [7-10]. Therefore, it is a controversial issue on the effectiveness of preventing SSI by using moist wound dressing versus conventional gauze dressing.

Ionic silver-containing dressing

Ionic silver (Ag⁺), is an active state silver oxidized biologically, is proved as a broad spectrum antimicrobial agent that is effective against aerobic, anaerobic, Gram-negative and Gram-positive bacteria, as well as fungi, viruses, and yeast with minimal development of bacterial resistance [7,8,11-13]. Silver is used commonly in many dressings for the antimicrobial effect. Silver containing dressing can reduce the inflammation of wounds and promotes healing, since silver cations in the dressing can destroy microorganism by inactivating bacterial enzymes, disrupting the functions of cell membrane and binding the bacterial DNA/RNA to cause cell death and inhibiting cell replication [12, 14-15].

Abdominal Colorectal surgery and ionic silver-containing dressing in Hong Kong

In Hong Kong, colorectal cancer is the commonest cancer, there were around 5000 new cases in 2014. And it is the second leading cause of cancer deaths, in 2015, around colorectal cancer caused 2000 deaths [16]. An unpublished internal audit carried out in surgical department in Princess Margaret Hospital (PMH) in 2015 found that the day 30 post-operation SSI incidence among patients with colorectal surgery using occlusive ionic silver-containing dressing (20%; 19/95) was statistically lower than those using conventional gauze dressing (52.9%; 9/17) with $p=0.012$ (Table 1). Although the effect of using silver dressing to reduce SSI rate is controversial, there are no formal study has been published locally. Therefore, it is meaningful to carry out a randomized controlled trial (RCT) to prove the significance of silver dressing in reduce SSI rate.

Table 1. Findings of unpublished internal audit in PMH on SSI among patients with colorectal surgery in 2015

	Conventional gauze dressing (n=17)		Occlusive ionic silver-containing dressing (n=95)		p value
	SSI	Incidence (95%CI)	SSI	Incidence (95%CI)	
Day 3	1	5.9% (1.0%-27.0%)	2	2.1% (0.6%-7.4%)	0.393
Day 15	8	47.1% (26.2%-69.0%)	14	14.7% (9.0%-23.2%)	0.005
Day 30	9	52.9% (31.0%-73.8%)	19	20% (13.2%-29.1%)	0.012

Objective

To compare the SSI incidence among patients with abdominal colorectal surgery patients using prophylactic occlusive ionic silver-containing dressing and conventional gauze dressing.

Methods

Study design and setting

This is a single-blind two-arm parallel randomized controlled trial on occlusive ionic silver-containing dressing conducted in Princess Margaret Hospital (PMH). PMH is a major acute general hospital in Kowloon West Cluster in Hong Kong, providing 1,542 beds to maintain a wide range of specialist care. There are around 150 abdominal colorectal surgery provided every year in our department. Both the subjects, data collectors and outcome assessors will be blinded to the type of dressing being used. Eligible inpatients receiving colorectal surgery from the department of surgery will be consecutively recruited in each surgical ward (namely, A4 ward, B4 ward and CD4 ward).

Subjects

Patient aged 18 years or above will be included if they undergo abdominal colorectal operation including colorectal cancer case and non-colorectal cancer case such as perforated diverticulitis, trauma, and so on. Patients with cognitive impairment and/or with known allergic reactions to silver, hydrofibre or hydrocolloid and/or with non-closed wound immediate after operation will be excluded.

Subjects will be randomly assigned to use occlusive ionic silver-containing dressing (experimental group) or conventional gauze dressing (control group) with equal probability. Blocked randomization will be carried out by an independent party using computer-generated random number sequences (www.randomization.com) in random blocks of two, four, six and eight, allocated in sequentially numbered, sealed opaque envelopes. Those envelopes would be prepared and placed in each surgical ward.

Data collection procedure

On the day of admission, or an emergency operation is offered, written informed consent will be obtained from all eligible patients. Patients will be arranged by an independent primary nurse in two groups, the experimental and control group, according to the designed block randomized sequence. Relevant dressing materials will be prepared by the primary nurse and bring to the operation theatre. In order to blind the subject, the incisional wound will be covered by ionic silver containing and hydrocolloid dressing with gauze covered on the top for the experimental group, whereas only gauze dressing will be applied for the control group.

Patient's case doctor will be responsible to document in data collection form, if there are surgical site infection occur. A research team is responsible for the data collection. Data obtained includes age, gender, pre-operative albumin level, pre- and post-operative sepsis status, operation class (elective or emergency), operation duration, number of operation, wound classification (clean, clean-contaminated, contaminated, and dirty), types of stoma raised (colostomy or ileostomy), the use and length of duration of antibiotics (pre op and post op). Subjects will be assessed for SSI on Day 3, 15 and 30 after operation in clinical area and followed by phone interviews. During hospitalization, patient's case doctor, who are independent to the study, will be responsible for outcome assessment. After patient discharge, patient will be provide the information of SSI status. Data will be collection by

Silver dressing RCT – protocol (Version 5; 14 September 2017)

research team via phone contact, patient will be blind to the study as well. Carers of the patient, who are blind to the study, will be interviewed if the patient is unable to describe their surgical site condition.

Outcomes

Primary outcome is the SSI on day 30 after operation, whereas secondary outcomes are day 3 and 15 SSI after operation. In view of updating patient's condition after the operation and removal of stitches, the secondary outcomes are decided on day 3 and 15 after operation. Assessment of SSI will adopt the basis of criteria developed by the Centers for Disease Control and Prevention (CDC) [17].

Statistical analysis

SSI incidence and relative risk with 95% confidence interval will be computed for the experimental and control groups. Differences in distribution of the clinical data and the development of an SSI in control and experimental groups were evaluated using Pearson's chi-square test, Fisher's exact test, independent t-test or Mann-Whitney U test, where appropriate. Statistical analyses will be performed using SPSS 22.0 for Windows (IBM Corp., Armonk, New York). A p value <0.05 will be regarded as statistically significant.

Sample size estimation

With reference to our previous internal audit, we might assume the day 30 SSI incidence in the experimental group and control group as 20% and 40%, respectively. Using PASS 13 for sample size calculation, the number of subjects needed in both groups will be 80 with a power of 0.8 and a significance level of 0.05. Assuming the response rate to be 80%, the total sample size required will be 200. It is estimated that the ratio of eligible patients in A4 ward, B4 ward and CD4 ward will be around 1:2:3, therefore the number of subjects needed will be 34, 66 and 100, respectively.

Ethical consideration

The protocol of this study will be submitted to KWC Research Ethics Committee for ethical approval and will be registered in ClinicalTrials.gov. Patients who meet the inclusion criteria will be given a comprehensive explanation of the wound dressing selection, including the experimental and control group, and the process of treatment allocation before the start of operation as well. Patient will be reassured the participation is voluntary and they may withdraw at any time during the study with no obligations. They will also be reminded that all detected SSIs are treated immediately and appropriately. Patients who developed an SSI will not be withdrawn from the study and will record as part of the data.

Data handling and record keeping

All data are for research purposes only. The data in paper form will be kept in a locked cupboard inside a locked room and the electronic data will be saved in encrypted file during the study. The hard copies of personal data will be discarded by shredding as confidential waste and all encrypted files with electronic personal data will be saved in CD-Rom for storage which will be destroyed at five

Silver dressing RCT – protocol (Version 5; 14 September 2017)

years after completion of the study. Principal investigator will be responsible for safekeeping of personal data during and after the study.

Publication

The research is for internal review and quality improvement but the publication right is still reserved.

Tentative time table

Protocol development	July 2017
Application of Ethical Approval	Aug 2017
Start of subject recruitment and data collection	Sep 2017
Interim analysis	Apr 2018
End of subject recruitment	Dec 2018
End of data collection	Jan 2019
Data cleaning and analysis	Feb - Mar 2019
Report writing	Apr - May 2019

References

[1] World Health Organization. Global Guidelines for the Prevention of Surgical Site Infection. Europe: WHO, 2016.

[2] Charles, K. F. & Morris, D. K. Overview of wound healing in a moist environment. The American Journal of Surgery 1994; 167(1): S2-S6.

[4] Chen, W. Y. J., Rogers, A. A. & Lydon, M. J. Characterization of biologic properties of wound fluid collected during early stages of wound healing. Journal of Investigative Dermatology 1992; 99(5): 559-564.

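### Envelopes are blocked within three wards but the day-30 comparison ignores ward, so its confidence interval is slightly too wide if SSI risk differs between wards (low priority)

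*Protocol*

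**What the plan says.** Under Methods, Study design and setting, patients are "consecutively recruited in each surgical ward (namely, A4 ward, B4 ward and CD4 ward"). Under Subjects, allocation to the silver dressing or "conventional gauze dressing (control group) with equal probability" is made "in random blocks of two, four, six and eight, allocated in sequentially numbered, sealed opaque envelopes", and then: "Those envelopes would be prepared and placed in each surgical ward". Under Sample size estimation, the expected ward ratio is "around 1:2:3, therefore the number of subjects needed will be 34, 66 and 100, respectively".

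Under Statistical analysis, "SSI incidence and relative risk with 95% confidence interval will be computed for the experimental and control groups", and differences are tested by "Pearson's chi-square test, Fisher's exact test, independent t-test or Mann-Whitney U test, where appropriate". Ward does not appear in the estimate or the test. The list of data items under Data collection procedure does not name ward either, but it is worded as a list of inclusions and need not be complete.

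**The concern.** Separate numbered envelope stocks, blocks of two to eight and a target for each ward keep the arms nearly equal within A4, B4 and CD4. Differences in SSI risk between wards then add almost nothing to the chance difference between arms. The pooled variance does not know this: it treats the between-ward spread as part of the random error. If ward risks differ, the stated interval is wider than it should be and the test rejects less often than its nominal 5%.

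What is at stake is a small, avoidable loss of precision in a trial with little power to spare. The validity of the comparison is not in question. Ward differences are conceivable because the trial mixes elective with emergency operations, cancer with non-cancer cases and clean with dirty wounds. The Protocol does not say how these are spread over the wards.

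**Working it through.** **The plan's own figure.** Inputs from Sample size estimation: 40% v 20%, power 0.80, significance level 0.05 (taken as two-sided; the text does not say).

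- Pooled variance: n = [1.96√(2×0.3×0.7) + 0.842√(0.24+0.16)]² / 0.2² = (1.270 + 0.532)² / 0.04, which gives 82 per group.
- Unpooled variance: 0.40×7.849/0.04 = 78.5, which gives 79.
- The stated 80 lies between these. Power at 80 per group is 0.794 by the pooled formula.
- 160/0.8 = 200. A 1:2:3 split of 200 is 33.3, 66.7 and 100, which the Protocol gives as 34, 66 and 100.

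**Formula.** Let w be the ward shares, p the ward risks and P = Σwp. With allocation balanced within wards, the true variance of an arm's proportion is Σwp(1−p)/n. The pooled formula uses P(1−P)/n. The gap is Σw(p−P)²/n, which is zero when wards are equal and otherwise positive. The pooled standard error (SE) can therefore be too large but not too small.

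**No dressing effect.** Ward shares are 0.17, 0.33 and 0.50, from 34/66/100. Ward risks are assumptions. Rejection rates are from 200,000 simulated trials at nominal 5%.

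| Ward risks A4/B4/CD4 | P(1−P) | Σwp(1−p) | Pooled SE / true SD | Pooled test rejects |
|---|---|---|---|---|
| equal | same | same | 1.00 | 5.1% |
| 50/30/20% | 0.2033 | 0.1918 | 1.03 | 4.4% |
| 10/30/50% | 0.2320 | 0.2096 | 1.05 | 3.9% |
| 60/40/15% | 0.2135 | 0.1838 | 1.08 | 3.6% |

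In a repeat with 400,000 trials, the Cochran-Mantel-Haenszel (CMH) test stratified by ward rejected 4.9 to 5.0% of the time throughout.

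**At the planned effect.** Shares are 1/6, 2/6 and 3/6, and the silver arm has half the control risk in each ward.

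- Control 60/45/30%: crude variance 0.24 + 0.16 = 0.4000; within-ward variance 0.2275 + 0.1569 = 0.3844. Ratio 1.041, or 2.0% in SE.
- Control 20/30/53%: crude 0.2397 + 0.1595 = 0.3992; within-ward 0.2212 + 0.1549 = 0.3761. Ratio 1.061, or 3.0% in SE.

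The Protocol's estimate is a relative risk, so each arm's term is divided by its squared risk to reach the log scale.

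- 60/45/30%: crude 0.24/0.16 + 0.16/0.04 = 5.500; within-ward 0.2275/0.16 + 0.1569/0.04 = 5.344. Ratio 1.029, or 1.5% in SE.
- 20/30/53%: ratio 1.044, or 2.2% in SE.

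Power at 80 per arm (normal approximation) is 79.9% crude v 80.8% stratified in the first case, and 79.8% v 81.3% in the second.

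**Simulation with the Protocol's block sizes.** Separate blocks of 2, 4, 6 and 8 in each ward, 160 patients split 27/53/80, 10,000 runs per row. Overall risks are held at 40% v 20% for power and at 40% in both arms for type I error.

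| Control risks | Type I error, pooled / CMH | Power, pooled / CMH | True SD / pooled SE, by formula |
|---|---|---|---|
| 40/40/40% | 0.048 / 0.048 | 0.807 / 0.803 | 1.00 |
| 30/37/45% | 0.046 / 0.048 | 0.798 / 0.799 | 0.99 |
| 20/33/51% | 0.042 / 0.049 | 0.805 / 0.814 | 0.97 |
| 10/25/60% | 0.028 / 0.048 | 0.820 / 0.855 | 0.91 to 0.92 |

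The simulation error of a power figure is about √(0.8×0.2/10,000) = 0.004, so the first two rows show no difference in power.

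**The case against.** The strongest reply is that nothing in the stated analysis is invalid. The pooled relative risk is unbiased, the test does not exceed its nominal level, and any loss depends on ward risks that the Protocol does not give. All three wards belong to one surgical department, and nothing in the text supports a four- to six-fold spread in risk. This stands, and it sets the priority.

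A second reply is that separate sequences per ward are inferred. The text never speaks of stratification, and Data collection procedure refers to the block sequence in the singular. That is fair, but envelopes stocked in each ward, with a target for each, make balance within ward the natural reading.

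A third is that stratification factors are often settled in a statistical analysis plan, which may exist but is not shown. The point here is not missing detail, however. The Protocol names its estimate and tests, and these do not match the allocation it describes.

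A reader might infer four stronger points that the document does not support:

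- **Ward as the site or operator unit.** An independent primary nurse prepares the dressing materials and takes them to theatre, so ward is not shown to be the unit that delivers the intervention.
- **An effect confined to one ward would be missed.** With 160 evaluable patients there are about 14, 26 and 40 per arm in the wards. Power for 40% v 20% within one ward is then only about 21%, 37% and 52%. A CMH test also does not test whether effects differ.
- **Ward is not collected.** The data list is open-ended, and ward targets with numbered envelopes suggest that ward can be recovered.
- **The interval is too narrow, as in a clustered trial.** Patients are randomised individually within wards, so the error runs the other way.

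**Conclusion.** The point holds as a minor mismatch between how patients are allocated and how they are compared. If ward risks differ by up to about 2.7-fold (the moderate cases above), the pooled standard error is about 1 to 3% too large, with 0 to 1.5 points of power lost. The excess is nearer 1.5 to 2% on the log relative risk scale for the two cases worked. Spreads of four- to six-fold give about 5 to 10%. The most extreme case, 10/25/60%, gives about 9%, a type I error near 0.03 and 3.5 points of power. With equal ward risks there is no loss.

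The error is conservative and does not bias the estimate. The sizes rest on assumed ward risks, near-equal arms within each ward, and the reading that blocks run within wards.

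**What to change.** Confirm that ward of randomisation is recorded for every patient. In Statistical analysis, make the primary day-30 comparison a Mantel-Haenszel relative risk with 95% confidence interval and a CMH test, stratified by A4, B4 and CD4. Keep the crude relative risk as a supporting result. Show SSI counts by arm within ward as description only. State under Subjects whether each ward has its own blocked sequence.

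The cost is at most one field on the form and two sentences of text, with no extra patients or procedures. If ward risks prove equal, practically nothing is lost (simulated power 0.803 v 0.807, within simulation error). The change should be made before outcome data are examined, so that it cannot look data-driven.

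### Allocation appears to come before surgery, yet a non-closed wound, known only when surgery ends, is an exclusion: an avoidable opening for selection after randomisation

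*Protocol*

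**What the plan says.** The order of steps has to be pieced together from several sections of the Protocol.

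- **Subjects (eligibility):** patients "with non-closed wound immediate after operation will be excluded".
- **Subjects (randomisation):** allocation is by numbered, opaque envelopes, of which the Protocol says: "Those envelopes would be prepared and placed in each surgical ward"; none are mentioned for theatre.
- **Data collection procedure:** consent is taken in writing at admission, or when emergency surgery is proposed. After that, "Patients will be arranged by an independent primary nurse in two groups", following the blocked sequence. Then comes the step that ties the arm to theatre: "Relevant dressing materials will be prepared by the primary nurse and bring to the operation theatre". The experimental arm receives the silver and hydrocolloid dressing with gauze on top; the control arm receives gauze only.
- **Study design and setting:** "Both the subjects, data collectors and outcome assessors will be blinded to the type of dressing being used". The operating team is not listed.
- **Ethical consideration:** patients are told about "the process of treatment allocation before the start of operation as well". This fixes when the process is explained, not when the envelope is opened.
- **Statistical analysis:** "SSI incidence and relative risk with 95% confidence interval will be computed for the experimental and control groups".

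No sentence gives the moment at which the envelope is opened, makes allocation wait for closure, or says what happens to an allocated patient whose wound is left open.

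**The concern.** Randomisation protects a comparison only if the patients compared are those who were randomised, or if any removals cannot depend on the arm. Here an eligibility criterion is settled at the end of the operation, while the arm seems to be fixed before it. The materials differ visibly between arms, and nothing in the Protocol conceals them from the team in theatre. Whether a wound is left open, or is recorded as non-closed, could therefore be decided with the arm known.

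The trial admits emergency cases, including perforated diverticulitis and trauma, and records contaminated and dirty wounds, so the criterion may well be used. If patients at high risk of infection were removed more often from one arm, the day 30 surgical site infection (SSI) incidence and the relative risk would favour that arm without any effect of the dressing. The direction is not predictable from the document; it could favour either dressing.

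**Working it through.** **Order of steps.** Preparing the materials relevant to a patient requires the arm to be known. The envelopes are held on the wards, and the nurse carries the materials from there to theatre. The natural reading is consent, allocation, surgery, closure, exclusion. A later opening of the envelope is not ruled out, but no sentence supports it.

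**The plan's own figures.** With 40% versus 20%, two-sided 5% and power 0.8, the unpooled normal approximation gives (1.960 + 0.842)² × (0.24 + 0.16) / 0.20² = 78.5, so 79 per group; the pooled version gives 82. The stated 80 is consistent with these, and 160 / 0.8 = 200. No planned figure is disputed.

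**Illustration under no true effect.** The Protocol supplies the 40% SSI rate and the 80 per group. Everything else is assumed: a share *s* = 20% of patients is high risk with SSI risk *h* = 70%; the others then have risk *o* = (0.40 − 0.2 × 0.70) / 0.8 = 32.5%; a fraction *f* of high-risk wounds is left open and excluded. The risk among those who remain is

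risk(*f*) = [*s*(1 − *f*)*h* + (1 − *s*)*o*] / [*s*(1 − *f*) + (1 − *s*)].

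- *f* = 0.1 (2% of the arm excluded): (0.126 + 0.260) / 0.98 = 39.39%
- *f* = 0.3 (6% excluded): (0.098 + 0.260) / 0.94 = 38.09%
- *f* = 0.5 (10% excluded): (0.070 + 0.260) / 0.90 = 36.67%

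One arm is held at *f* = 0.1. The relative risk is that of the arm with more exclusions over the arm with fewer. The type I error comes from exact enumeration of the two-sided Pearson chi-square test, with 80(1 − 0.2*f*) patients per arm, rounded.

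| Excluded, by arm | n | Shift (points) | Relative risk | Type I error |
|---|---|---|---|---|
| 2% vs 2% | 78 vs 78 | 0 | 1.00 | 0.0513 |
| 2% vs 6% | 78 vs 75 | 1.30 | 0.967 | 0.0543 |
| 2% vs 10% | 78 vs 72 | 2.72 | 0.931 | 0.0616 |

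**Sensitivity to the assumptions** (same two unequal scenarios, *f* = 0.1 vs 0.3 and 0.1 vs 0.5):

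- *h* = 60%: 0.87 and 1.81 points; type I error 0.0526 and 0.0541.
- *h* = 80%: 1.74 and 3.63 points; type I error 0.0567 and 0.0723.
- High-risk share 40%, *h* = 70%: 2.84 and 6.25 points; type I error 0.065 and 0.123. Here 4% of one arm and 12% or 20% of the other are excluded.

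**The case against.** The case against is that the timing is inferred, since no sentence says when the envelope is opened. Bias also needs two further links: the team must learn the arm before closing, and that knowledge must change whether the wound is closed or is called non-closed. The Protocol shows neither, and it is not obvious why the choice of dressing should influence closure. The numbers depend entirely on assumed rates and an assumed imbalance, and even equal exclusion gives 5.13%, so the first two increments are only about 0.3 and 1.0 percentage points. Finally, how excluded patients are analysed may be settled in an analysis plan that is not at hand.

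Most of this stands as a limit on the claim. The figures describe what an imbalance would do, not what is expected here, and surgeons missing from the list of blinded persons is no evidence of selective closure. What does not fall is the order of steps. The text as written puts an exclusion after allocation, and nothing elsewhere corrects it. That is trial conduct rather than analysis: an analysis plan cannot recover patients who were excluded and not followed.

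**Conclusion.** The point holds as a minor design weakness. The Protocol implies allocation before surgery and applies an exclusion that can be judged only after it, with no stated concealment from the operating team. This is an opening for selection, not a demonstrated bias: if exclusion is unrelated to arm, the comparison stays valid.

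Under the assumed scenarios with a 20% high-risk share, the spurious difference ranges from 0.9 to 3.6 points, against a planned 20 points (relative risk 0.50). Doubling that share slightly more than doubles the shifts. All open-wound rates, the high-risk share and the risks by stratum are assumptions, because the document gives none.

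**What to change.** **Preferred change.** Amend the data collection procedure so that both dressing sets are available in theatre and the next numbered envelope of the ward's series is opened only once the wound is declared closed. Use envelopes in order of closure, which covers two patients of one ward in theatre at the same time. Log patients with a non-closed wound as screened and not randomised. The amendment should name who opens the envelope; the independent primary nurse who already brings the materials to theatre would fit.

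*Cost:* one paragraph of text. The planned 80 per group and 200 in total stand, and the explanation to patients before the operation can stay as it is. The burden is practical: envelopes, both dressing sets and the person opening the envelope must be at hand, including for emergencies. Staff present at opening learn the arm, but only after closure.

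**If allocation must stay before surgery.** Follow every allocated patient, report non-closed wounds by arm and analyse all as randomised, stating that this replaces the exclusion. This is more of a trade-off, because it changes the target population and includes some patients who may not receive the study dressing. If a proportion *x* in both arms has a non-closed wound and an SSI risk that does not depend on arm, the planned difference becomes 20 × (1 − *x*): 19.6, 18.8 or 18.0 points for *x* = 2%, 6% or 10%.

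### Possible improvement, not an error: adjust the day-30 SSI comparison for operation class and pre-operative albumin, which are already collected, for about 0 to 7 points of power over the planned chi-square test

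*Protocol*

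**What the plan says.** The Statistical analysis section of the protocol gives the effect measure: "SSI incidence and relative risk with 95% confidence interval will be computed for the experimental and control groups". For testing it says "Differences in distribution of the clinical data and the development of an SSI in control and experimental groups were evaluated using" a choice of chi-square, Fisher, t or Mann-Whitney tests. The threshold follows: "A p value <0.05 will be regarded as statistically significant". No covariate, regression model or stratified analysis is named, so the relative risk reads as unadjusted, although the protocol does not use that word.

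The Data collection procedure lists among the recorded items "pre-operative albumin level, pre- and post-operative sepsis status, operation class (elective or emergency" as the alternatives for the last of these. It gives the order of events as consent first ("On the day of admission, or an emergency operation is offered, written informed consent will be obtained from all eligible patients"), then allocation by the primary nurse, then "Relevant dressing materials will be prepared by the primary nurse and bring to the operation theatre".

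The Subjects section admits a mixed population, "including colorectal cancer case and non-colorectal cancer case such as perforated diverticulitis, trauma, and so on". The Outcomes section makes SSI on day 30 primary. The Tentative time table has an interim analysis in April 2018.

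**The concern.** Eligible patients range from cancer surgery to perforated bowel and trauma, so their risk of SSI may differ before any dressing is applied. The documents do not say by how much. If operation class and albumin predict SSI, a comparison that ignores them is less precise than it could be. Under the stated tests the two items are only compared between the groups, which does nothing for the treatment estimate.

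Both items suit adjustment. They can be known when the envelope is opened, and a dressing applied at the end of surgery cannot alter them.

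The sample size has little slack (see the working), so precision from data already on the form would be welcome. At stake is a modest amount of power. The validity of the trial is not in question.

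**Working it through.** **Inputs from the protocol (Sample size estimation):** day-30 SSI 40% control and 20% experimental; 80 per group; power 0.8; significance level 0.05 (taken as two-sided); 80% response; 200 in total.

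**1. Reproduce the plan's figure.** The mean rate is 0.30.
- Pooled variance: n = [1.960·√(2·0.30·0.70) + 0.8416·√(0.40·0.60 + 0.20·0.80)]² / 0.20² = (1.270 + 0.532)² / 0.04 = 81.2, so 82 per arm.
- Unpooled variance: (1.960 + 0.8416)²·0.40 / 0.04 = 78.5, so 79 per arm.
- The stated 80 lies between these, and 160 / 0.8 = 200. The sample size reproduces and belongs to an unadjusted comparison of two proportions.
- Power at 80 per arm: Φ[(0.20 − 1.960·√(0.42/80)) / √(0.40/80)] = Φ(0.820) = 0.794. By exact binomial calculation the chi-square test has power 0.801.

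**2. Precision of the unadjusted relative risk.** SE(log RR) = √[0.6/(0.4·80) + 0.8/(0.2·80)] = √0.06875 = 0.262, giving an interval of about 0.30 to 0.84 around 0.50.

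**3. What adjustment does to the variance.** Simulation with 4,000 trials per setting, 80 per arm and 30% emergencies (assumed). The ratio is var(log RR standardised from a logistic model with group, class and albumin) over var(unadjusted log RR). Odds ratios (OR) are for emergency v elective and per SD lower albumin.
- OR 1 and 1: 1.01
- OR 1.5 and 1.25: 0.99
- OR 2 and 1.5: 0.96
- OR 3 and 2: 0.89

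**4. Power against the planned test.** The protocol declares significance by p value, so the fair comparator is the chi-square test. Simulation with 4,000 trials per setting, 80 per arm, 40% v 20% and 40% emergencies (assumed):

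| Assumed strength (class OR, albumin OR per SD) | Chi-square | Adjusted RR, Wald (robust Poisson) | Adjusted likelihood-ratio test (logistic) | LR test minus chi-square (points) |
|---|---|---|---|---|
| None (1, 1) | 0.806 | 0.788 | 0.806 | 0.0 |
| Weak (2, 1.2) | 0.807 | 0.798 | 0.813 | +0.6 |
| Moderate (2, 1.5) | 0.797 | 0.805 | 0.820 | +2.3 |
| Moderate (3, 1.5) | 0.804 | 0.820 | 0.837 | +3.3 |
| Strong (5, 2) | 0.804 | 0.858 | 0.872 | +6.8 |

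The Monte Carlo SE of a single power is √(0.8·0.2/4000) = 0.006. Type I error of the likelihood-ratio test was 0.048 to 0.055. With a Monte Carlo SE of √(0.05·0.95/4000) = 0.003, that is compatible with 0.05.

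**5. Why the form of the test matters.** A Wald test of the adjusted relative risk falls below chi-square by 1.8 points with no prognostic value (0.788 − 0.806) and by 0.9 if weak (0.798 − 0.807). The loss comes from the Wald test and not from adjusting. Without any adjustment, the relative-risk interval already has exact power 0.788 against 0.801 for chi-square. The likelihood-ratio test avoids the loss.

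**6. Model size.** Expected events are 0.20·80 + 0.40·80 = 16 + 32 = 48. With three terms that is 16 per term.

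**The case against.** The strongest objection is that nothing here is wrong. A chi-square test and an unadjusted relative risk are valid in a 1:1 randomised trial and agree with the 80-per-group calculation. Covariates and model details commonly sit in a statistical analysis plan, and one that was not available for this review may already name them. All of this stands. A reader might infer that the stated analysis is biased, underpowered or incomplete. The documents support none of these: randomisation protects the unadjusted comparison, the sample size reproduces, and the protocol does not rule out adjustment.

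A second objection is that the gain looks larger when set against the relative-risk interval, which is weaker than the chi-square test. This also stands, and the figures here are therefore against chi-square. It also rules out a Wald test of the adjusted relative risk as the primary test.

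Third, the benefit is assumed. A mixed case load shows that patients differ, not that these two variables predict SSI. This stands as a limit on size. It does not remove the point, because with the likelihood-ratio test the cost in power is about nil if the assumption fails.

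A reader might also count it as a flaw that the p value and the interval come from different methods. It is not. At 40% v 20% the chi-square test and the unadjusted relative-risk interval disagree on significance in about 1.3% of trials (exact calculation), which is ordinary.

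**Conclusion.** An optional improvement that holds, of low priority. Against the planned chi-square test it is worth about 0 points of power if neither factor predicts SSI, about +1 if weak, +2 to +3 if moderate and about +7 if strong, with type I error about 0.05.

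The size depends on assumptions that the documents cannot confirm: the odds ratios, 40% emergencies, 160 evaluable patients and complete albumin values. The strong setting in particular has no support in the documents and marks only the upper end of the range. Confidence is good that adjustment by this test does no appreciable harm, and only moderate that it helps noticeably.

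**What to change.** If the team wants the gain, add to the Statistical analysis section, before any outcome is seen and so before the interim analysis:

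*The primary p value for day-30 SSI is the likelihood-ratio test for group in a logistic regression with terms for group, operation class (elective/emergency) and pre-operative albumin. The relative risk with 95% CI is standardised from the same model. A missing albumin value is replaced by the mean of all observed values, both groups together, so that no patient is dropped. The unadjusted relative risk and chi-square test are supportive.*

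Do not adjust for anything recorded after allocation, such as post-operative sepsis or post-operative antibiotics. If an analysis plan already specifies adjustment, check it against this and change nothing else.

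The cost is four sentences, with no extra patients and no new data items. Four small burdens remain:
- slightly more analysis work;
- the missing-albumin rule;
- a check on the software, since the protocol says "Statistical analyses will be performed using SPSS 22.0 for Windows" and it must be confirmed that this gives the interval for a standardised relative risk;
- occasional disagreement between the likelihood-ratio p value and the relative-risk interval. It should be rare, as it already is for the unadjusted pair, but its rate was not computed.

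A Wald test of the adjusted relative risk should not be the primary test. It would cost about 1 to 2 points against chi-square if the factors are weak or not prognostic.
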